4.0 DRUG/DEVICE INFORMATION

4.1 DRUGS

The only drug to be used is optional generic acetaminophen in recommended dose.

- 4.1.1 Standardized amounts of non-prescription nutrients and electrolyte solution will be administered both orally and via NJ tube.
 - 4.1.1.1 High Protein Shake ® Abbott Park, Illinois, U.S.A. All subjects will take 800mls divided equally and administered 4 times a day. This will provide the following each day: 100% of RDA high quality protein, 400kcal, 800mls water, 20% of potassium requirements and 16% of sodium requirements (Per 14 fl oz. bottle: 210 calories, protein 25g, carbohydrate 23g, fat 2.5g, sodium 240mg, potassium 290mg)
 - 4.1.1.2 Unflavored Pedialyte ® Abbott Park, Illinois, U.S.A. All subjects will take 800mls of Pedialyte /day divided equally and administered 4 times a day. This will provide the following each day: 80kcal, 800mls water, approx. 40% of potassium requirements and 40% of sodium requirements. (Osmolality, mOsm/kg H₂O: 250; per liter: Sodium, mEq: 45; Potassium, mEq: 20; Chloride, mEq: 35; Zinc, mg: 7.8; Dextrose, g: 25; Calories: 100). No artificial sweeteners or flavors.
 - 4.1.1.3 The only difference is that the intervention group will receive the High Protein Shake via the tube and take the Pedialyte orally whereas the control group will take the Pedialyte via tube and the High Protein Shake by mouth.
 - 4.1.1.4 Klor-Con 1 tablets 10meq/tab. All subjects will take 2 tablets/day which will provide remaining potassium requirements (approximately 30-50% of RDA).
 - 4.1.1.5 Table salt (generic): All subjects will take 3grams/day (half a teaspoon) to provide remaining sodium requirements (approximately 30-50% of RDA).
- 4.1.2 Kirkland Signature Daily Multi Vitamins & Minerals 1/day will provide 50-100% of RDA
- 4.1.3 Kirkland Signature Calcium 600 Mg + D3 500 Tablets 2/day will provide 80-100% of RDA
- 4.1.4 Liquid acetaminophen (generic) 500mg/15mls: if desired for throat pain. Maximum 60mls/day.
- 4.2 Glucose tablets (generic) 15g: to be carried at all times for use in the event of hypoglycemia.
- 4.3 For anesthesia of the pharynx if requested by the study participant and no contraindication: viscous lidocaine 2% (generic): 5 mL gargled for 3 minutes and may be swallowed. One dose only 5minutes prior to the procedure. The maximum dose for this agent is no more frequently than every 3 hours with a maximum of 8 doses per 24-hour period.[34] Contraindication: Hypersensitivity to lidocaine or any component of the formulation; hypersensitivity to another local anesthetic of the amide type.

4.4 DEVICE

CORTRAK® 2 ENTERAL ACCESS SYSTEM (EAS™) [35-41]

This system is FDA cleared for placement of enteral feeding tubes without x-ray confirmation. A transmitting stylet is used to place the enteral tube. The tip of the stylet contains an electromagnetic transmitter that generates a real-time signal as the feeding tube is inserted and advanced to the desired placement. The signal from the transmitting stylet is tracked throughout the placement procedure via a lightweight receiver unit (Smart Receiver Unit: SRU) that is placed on the patient's xiphoid process. A monitor triangulates the signal from the SRU and displays a real-time representation of the feeding tube tip's passage as it proceeds down the esophagus and into the preferred placement position — gastric, duodenal, or jejunal. (See

Fig 6)

Fig 6

Advantages of **CORTRAK® 2 ENTERAL ACCESS SYSTEM (EAS™)**

Safe

- Eliminates or significantly reduces patient exposure to X-ray
- Confirms accurate placement quickly
- Clinicians are able to identify misplaced tubes immediately to significantly reduce adverse events

Accurate

- In a multi-center study 99.5% of placements correlated with abdominal X-ray
- 89% -100% success rates reported with gastric, jejunal, and duodenal placement
- Additional depth cross-sectional view may more accurately predict location compared with X-ray

Fast

- Real-time visualization of the relative tube tip position eliminates waiting time for X-ray confirmation

Support

- CORTRAK's Clinical Educators assist with implementation planning, on-site education training programs and customized protocol development with hospital education teams
- CORTRAK 2 Learning Center at www.cortraksystem.com provides high-quality, on-demand training and training checklist, link to Mosby's Nursing Skills)

Flexibility

- Choice of operating mode for easy upload of data for training, review, or research
- 2D and 3D views provide more information than X-ray for confident placement without X-ray

Evidence

- Growing clinical research base demonstrating system's safety and efficacy
- Used by more than 200 healthcare systems worldwide

Of note the PI and CoI have been trained and certified in use of the EAS and have been using it in preliminary studies in outpatients. To date they have placed approximately 25 jejunal tubes with this system without incidence.

Intraoral Anchor (see Fig 7)

For the purposes of this study we will secure the tube intraorally rather than through the nasopharynx to the skin.

[figure not shown]
The rationale for this is:

- To minimize discomfort to the subject due to placement of the tube through the sensitive nasopharynx
- To eliminate the risk of complications in the nasopharynx such as nose bleed, sinusitis and malposition
- To improve social acceptability of the study by rendering the tube inapparent to the casual observer.
- To simplify tube maintenance by avoiding the need for taping or other means of securing the tube externally.

To achieve this we will:

- a. Modify a standard orthodontic molar band on an upper molar with the addition of a metal channel to anchor the tube in the mouth. The channel is welded to the buccal surface of the band.
- b. Place standard orthodontic spacers following standard orthodontic procedure on either side of the selected molar
- c. Approximately 1 week later place the modified molar band
- d. Modify a standard CORPAK enteral feeding tube by cutting off the access port and leaving only an approximately 4mm flange
- e. Pass the tube through the channel in the alert subject so that the tube passes through the lateral oropharynx and then, by standard placement technique, to the jejunum
- f. Fashion an integrated tube cap to close the tube when not in use
- g. Provide a syringe with a blunt tapered tip to administer fluids per protocol.

Fig 7

- b. The modified molar band is a minor variant of standard orthodontic molar band and is very secure and similarly renders the risk of distal displacement of the tube extremely low.
- c. The tube position in the oropharynx is lateral to sites triggering the gag reflex and allows for virtually normal speech, swallowing and eating with minimal or no gagging and is virtually undetectable by others.
- d. Some discomfort and mild pain (maximum ~4 out of 10) can be expected mostly in the first 4-5 days of use. This can be eased with several maneuvers including change of body position and acetaminophen in standard dose.
- e. The discomfort and pain can be expected to be minimal after the first 5 days such that the subject is barely aware of the tube's presence.
- f. There is minimal risk of throat or gastrointestinal complications with a 10 French jejunal tube placed in the described manner and for duration of 2 weeks.

5.0 SELECTION AND WITHDRAWAL OF RESEARCH SUBJECTS

5.1 Inclusion Criteria:

- 18-70 years of age
- Type 2 diabetes on oral antidiabetic medication
- BMI ≥ 30 kg/m²
- A1C <9%

5.2 Exclusion Criteria:

- Use of any of the following medications: dipeptide-peptidase IV (DPP-IV) inhibitors (e.g., sitagliptin), GLP-1 analogs (e.g., exenatide) or medication that could alter glucose tolerance (e.g. steroids)
- Contraindication to tube (e.g. Prior upper gastrointestinal bleed, or history of easy bleeding, altered foregut anatomy due to obstruction or surgery)
- Known cardiovascular disease other than controlled hypertension.
- Pregnancy or unwilling to take contraception
- Active esophagitis
- Known hiatal hernia
- Active gastric ulcer and/or duodenal ulcers,
- Previous restrictive surgery of the gastrointestinal tract
- Crohn's disease
- Active cancer
- History of gastrointestinal hemorrhage

- Known upper gastrointestinal lesions with potential to bleed
- Use of NSAIDs or anticoagulants
- Psychiatric disorders other than mild depression
- Likely inability to adhere to study protocol including alcohol or drug dependent patients
- Type I diabetes,
- Liver, kidney or multi-organ dysfunction.
- Known eating disorders
- Inability to attend scheduled or unanticipated study visits
- Known prior abdominal problems or operations that could lead to adhesions or strictures and that could prevent the spontaneous passage of a 10 French jejunal tube if it were to dislodge distally.

5.3 Withdrawal Criteria

- Non-adherence to study instructions by subject for more than 2 days.
- Any request by subject
- Fever over 100.4 F, more than 1 episode of vomiting, gastrointestinal upset not relieved by reduction in tube feed, dislodged anchor or tube, average daily glucose over 200mg/dL on 2 or more days, weight change of >7% in first week of tube use.
- Clinical judgment of the PI (reason to be specified)

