Day 0: Subject presents fasting to the CHC. Blood pressure, heart rate, weight, height and waist circumference and body composition on InBody520 BioSpace will be recorded. FitBit® activity monitor placed. Subjects will have a jejunal feeding tube placed by the investigator using a CORPAK EAS™ and will then be randomized to the control or intervention group.

Day 0-Day 14: Subjects will take a mixed meal or electrolyte solution at a prescribed rate and interval and will be requested to eat ad lib only from provided meals of known caloric amount or from a list of low calorie items. Subjects will maintain a log of all food intake, temperature at least daily, tube position and symptoms and blood glucose 4 times a day.

Day 7: The subject will return to the CHC for review for continuation in the study, of their log and caloric intake and for adjustment of medication if necessary and activity monitor download.

Day 14: Day 0 measures will be repeated at the CHC and the tube removed. All uneaten food will be returned for caloric intake determination, activity monitor download.

Day 15-Day 28: The subject will maintain a medication and blood glucose log for 14 days after the removal of the tube.

Day 28: Exit outcome measures similar to those at Day 0.

Safety: The subjects will be monitored for fever, sore throat, displacement of the tube, gastrointestinal upset, vital signs, biochemical measures and weight change, and if pre-specified criteria are met or in the clinical judgment of the PI it is not appropriate to continue, will be withdrawn from the study.

Outcome Measures: weight change, caloric intake, waist and hip measurement, hormones and biochemical measures, physical activity, body composition, select symptoms, medication use, average self-monitored blood glucose level

Reimbursement: Subjects will receive standardized meals of known caloric amount for 2 weeks and up to \$300 cash.

Statistics This is a pilot study and sample size estimates are not appropriate. However based on studies of dietary restriction with a 1250 kcal diet for 1 week we anticipate identifying a significantly greater weight loss in the intervention arm with a sample size of 10 subjects/group. Fifteen subjects/group will be enrolled to allow for drop-outs.

Analysis: Primary analysis will be to compare change from baseline in outcome measures between the 2 groups using paired t-test. SC CTSI Biostatistics Department has aided in the study design.

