There may be as little as 2 days or as long as several weeks from the time the spacers are placed to the time the tube is placed depending on subject and study team member availability and technical aspects of the band and tube placement (i.e. how long it takes for the spacers to separate the teeth adequately, whether the subject requires 1 or 2 visits to fit the molar band and whether the subject has the tube placed the same day as the molar band).

Day 0: The subject will be seen at the CHC in the fasted state. All women between 18 and 50 years of age who have not undergone hysterectomy or tubal ligation will undergo a urine pregnancy test. If the test is positive then they will not be eligible to participate. Baseline vital signs, weight, height and waist and hip circumference will be recorded and baseline labs drawn. Body composition will be measured by the Biospace InBody 520 device (Biospace, Cerritos CA 90703 <http://www.biospaceamerica.com/>). This device measures body composition non-invasively as the subject stands on a scale-like device while grasping two handles – one in each hand. The device works by sending a very low voltage electrical signal through the body to determine water content, body fat percentage, and lean mass. The machine will be kept in the basement of the CHC. The FitBit Monitor is placed on the subject's wrist or clothing and will record activity for up to 2 weeks at a time without need for any adjustment by the wearer.

Body weight will be measured in the morning on a calibrated scale with the subject wearing light clothing. Waist circumference will be measured by wrapping a flexible measuring tape around the narrowest point of the midsection. The tape will be kept parallel to the floor. Hip circumference will be measured by wrapping a flexible tape around the hips at the widest diameter of the buttocks. The tape will be kept parallel to the floor. The waist-to-hip ratio will be determined by taking the waist circumference and dividing by the hip circumference.

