- As subjects adhering to very low-calorie diets usually have a fall in blood pressure, especially during the first week antihypertensive drugs will be discontinued unless moderate to severe hypertension is present.[33]

- Subjects will be requested to be as physically active as they like. Thus they are at liberty to increase, decrease or maintain their usual activity level.
- Similarly as most diabetic patients eating very low-calorie diets have marked improvement in hyperglycemia with blood glucose concentrations falling within the first one to two weeks oral hypoglycemic drugs will be discontinued for the first week of therapy. [33] An increase in activity level may also cause a fall in blood glucose levels. To aid in maintaining safe blood glucose levels subjects will be required to report to the study team if their blood glucose is over 250mg/dl on more than 2 consecutive measures or any value over 300mg/dl or less than 70mg/dl on any occasion. Symptoms of hypoglycemia (sweating, weakness, palpitations, confusion) will be reviewed with the participant at each visit. They will be advised to check their blood glucose if possible if such symptoms occur and to take one 15g glucose tablet (to be carried at all times) and repeat this every 15minutes until self-monitored blood glucose is over 80mg/dL or symptoms resolve.

Table 3 Summary of Nutrient Administration Days 0-Day 14

Item:	Intervention Group:	Control Group:
Ensure High Protein Shake (400kcal/800mls/100% protein RDA/day)	Via tube*	By mouth
Unflavored Pedialyte Electrolyte Solution (80kcal/800mls/~50% electrolytes/day)	By mouth**	Via tube*
Additional vitamins and electrolytes	By mouth	By mouth
Ad Lib food from that provided	By mouth	By mouth
Ad Lib “calorie-free” foods from provided list	By mouth	By mouth

*If unable to administer by tube the remainder to be taken by mouth

**Optional artificial flavoring (provided) may be added by subject if they wish to the orally ingested Pedialyte to increase palatability. This will be documented in the daily log.

Day 7: Subjects will return to the clinic for review of log and caloric intake. Medications will be triturated at the study clinician’s discretion in an attempt to attain euglycemia. The position of the tube tip will be assessed per FDA approved procedure by reinsertion of the subject’s own transmitting stylet and the tube will be repositioned if not located beyond the Ligament of Treitz.

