Day14: Baseline measures will be repeated. The position of the tube tip will be assessed per FDA approved procedure by reinsertion of the subject’s own transmitting stylet and then removed. All uneaten food will be returned for caloric intake determination, activity monitor download.

Day 15-Day 28: The subject will maintain a symptom and blood glucose log for 14 days after the removal of the tube.

Day 21: Subjects will return to the clinic for review of log and activity monitor. Medications will be titrated at the study clinician’s discretion in an attempt to attain euglycemia.

Day 28: Exit outcome measures similar to those at Baseline and Day 14.

Possible Additional Study Visits: Subjects will be seen at additional visits by the study team if they so request or if deemed appropriate by the study clinicians. Subjects will be encouraged to contact the study team if they do not feel well or if certain criteria are met. These specific criteria are:

- Self monitored blood glucose values over 200mg/dL on 3 scheduled checks
- Failure to ingest prescribed amounts of fluid
- Failure to administer tube feed on 2 successive occasions
- A morning oral temperature reading >37.2°C (98.9°F) or an afternoon temperature of >37.7°C (99.9°F)
- Pain that does not resolve spontaneously over 3 or 4 hours or with use of acetaminophen

Additional visits may be scheduled to determine position of the tube or to reposition the tip if it was not successfully placed in the jejunum at the initial visit or if the tube is blocked in which case attempts will be made to unblock it or it may be replaced.

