9.0 CLINICAL AND LABORATORY EVALUATIONS AND STUDY CALENDAR

Table 5

	Preparation			With Tube		Follow Up	
	Approximately Day-14	Approximately Day -7	Day 0	Day 7	Day 14	Day 21am	Day 28
Location ALL at EDWARD R. ROYBAL CHC							
Clinical Evaluation	By orthodontist for suitability for molar band	By orthodontist for placement of molar band (may require 2 visits)	By MD Vital Signs Symptoms Physical Exam Weight Waist Hip	By MD Vital Signs Symptoms Physical Exam Weight Waist Hip	By MD Vital Signs Symptoms Physical Exam Weight Waist Hip	By MD Vital Signs Symptoms Physical Exam Weight Waist Hip	By MD Vital Signs Symptoms Physical Exam Weight Waist Hip
Labs (total 20 cc/visit)	none	none	BMP ^a Fasting: Adiponectin ^b Leptin ^b FGF-19 ^b Insulin ^b Glucose ^b C-peptide ^b GLP-1 ^c Ghrelin ^c PYY ^c CCK ^c Bile Acids ^c FT3 ^c		BMP ^a Fasting: Adiponectin ^b Leptin ^b FGF-19 ^b Insulin ^b Glucose ^b C-peptide ^b GLP-1 ^c Ghrelin ^c PYY ^c CCK ^c Bile Acids ^c FT3 ^c		BMP ^a Fasting: Adiponectin ^b Leptin ^b FGF-19 ^b Insulin ^b Glucose ^b C-peptide ^b GLP-1 ^c Ghrelin ^c PYY ^c CCK ^c Bile Acids ^c FT3 ^c
Procedure	Place spacers	Place band	Place tube Place FitBit Body Composition Provide 1 week food	Return all uneaten food Provide 1 week food	Return all uneaten food Remove tube and band Body Composition		Remove FitBit Body Composition
Other Activities	none	Start Daily Flow Sheet	Review daily flowsheet including self-monitored blood glucose	Review daily flow sheet including self-monitored blood glucose Download FitBit/recharge	Review daily flow sheet including self-monitored blood glucose Download FitBit/recharge	Review daily flow sheet including self-monitored blood glucose Download FitBit/recharge	Review daily flow sheet including self-monitored blood glucose Remove and download FitBit
Food Intake	Ad lib		Day 0-Day 14 Tube Bolus and Provided Diet Ad lib free foods Supplements		Day 14-Day 28 Ad lib		

^aat USC DORI ^bat Cedars-Sinai ^cat Cedars Sinai when funds available

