10.0 CRITERIA FOR EVALUATION AND ENDPOINT DEFINITIONS

Primary aim: weight change immediately following the intervention period between the study groups

Secondary aims: to compare the following within and between groups:

- a. From Day 0 to Day 14: caloric intake (as determined by consumption of provided food)
- b. From Day 0 to Day 14: weight change (within group)
- c. From Day 0 to Day 28: weight change
- d. From Day 0 to Day 14 and also from Day 0 to Day 28: waist and hip measurement, hormones and biochemical measures, physical activity, body composition, select symptoms, medication use, average self-monitored blood glucose level

11.0 SPECIAL INSTRUCTIONS:

Samples will be collected by the PI or IRB approved research assistant from peripheral venipuncture.

The investigator will draw 20cc fasting blood at Day 0, 14 and 28 visits into a prepared tube containing aprotinin. This will be kept on ice and centrifuged, separated and aliquoted within 30mins of blood draw. Samples will then be stored at -20 degrees centigrade until transferred on ice to collaborator for assay.

Study Costs: All costs for this study will be paid from study funds. There will be no patient care costs incurred for payment from non-study funds. Costs covered by the study include study visits, supplies, equipment, blood draws, biochemical analysis and subject reimbursement.

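### Nothing keeps the arm from the staff who tape waist and hip or from the PI who may withdraw subjects on judgment, though partial masking of those two tasks would be cheap

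*Combined protocol and SAP*

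**What the plan says.** Section 5.3 lists mostly fixed events and thresholds for withdrawal, then adds "Clinical judgment of the PI (reason to be specified"). The Safety paragraph of the synopsis repeats this: a subject for whom "in the clinical judgment of the PI it is not appropriate to continue, will be withdrawn from the study".

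Table 5 in section 9.0 heads the clinical evaluation at Days 0, 7, 14, 21 and 28 with "By MD Vital Signs Symptoms Physical Exam Weight Waist Hip". Section 3.0 (Day 0) gives the method: "Waist circumference will be measured by wrapping a flexible measuring tape around the narrowest point of the midsection". Hip is also taken by tape. Weight is read from a calibrated scale in the morning, in light clothing.

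The synopsis has the investigator place the tube and the subject randomized afterwards. Section 3.0 has the first bolus taken before the subject leaves. No available page says that any clinician, measurer or subject is unaware of the arm, and the word blind is used only of tube intubation. Some pages, apparently including the Appendix B subject instructions, were not available.

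The arms are closely matched. Table 3 and section 4.1.1 give every subject the same two liquids, 800 mL of each daily, and only the route differs. The fixed rows of the Appendix C log refer to the tube feed and the required oral feed without naming the product.

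**The concern.** A tape held at the narrowest point of the midsection depends on the person holding it. Someone who knows the arm, and knows which arm is expected to shrink, can shift the reading without intending to. Waist and hip are named secondary outcomes in section 10.0.

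A withdrawal on judgment is likewise open to knowledge of the arm. If such subjects then drop out of the Day 14 comparison, the set being compared has been partly chosen by someone who may know the allocation. With about 10 per group expected, a couple of decisions matter. Section 13.0 says the effect estimates will feed the design of later studies, so a bias here would carry forward even though this is a pilot.

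The design already goes to some trouble to match the arms, because section 1.0 argues that a tube and a non-nutrient liquid can themselves alter intake. Leaving the measurer and the withdrawal judge free to know the arm gives up part of what that matching could deliver.

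**Working it through.** The plan has no figure of its own on this point. The check has two parts.

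**1. Which outcomes are exposed**

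| Outcome | How obtained | Exposure to knowledge of arm |
|---|---|---|
| Waist, hip | Tape, by a physician (3.0, Table 5) | Direct |
| Weight (primary) | Calibrated scale (3.0) | Little in the reading; possible through who remains |
| Body composition, activity, assays | Device, FitBit, laboratory (3.0, Table 5) | Little |

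**2. Size of the withdrawal route (illustration)**

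Inputs:
- The synopsis enrols 15 per group and expects 10, an attrition allowance of (15 − 10)/15 = one third. I take 12 per arm as an intermediate assumption.
- Assume 2 of 12 intervention subjects are withdrawn on judgment, no controls are, and the withdrawn are left out of the analysis.
- The documents give no SD. Table 2 in section 1.0 reports losses of 7.26 kg (6.41 to 8.11) on diet and 3.95 kg (1.7 to 6.2) after surgery plus diet, N=10. Assuming these are 95% confidence intervals, SD = half-width / 2.262 × √10. That is 0.85/2.262 × 3.162 = 1.19 kg and 2.25/2.262 × 3.162 = 3.15 kg.

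Formula: the two smallest of 12 standard normal values have expectations −1.629 and −1.116. If the withdrawal decision correlates ρ with weight loss, removing the two lowest-scored subjects raises the arm's mean loss by

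ρ × (1.629 + 1.116)/(12 − 2) = ρ × 0.274 SD.

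False-positive rates come from simulation with no true effect, 10 versus 12 subjects and a two-sided t-test at 0.05.

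| ρ | Shift | kg, SD 1.19 to 3.15 | p<0.05 favouring intervention |
|---|---|---|---|
| 0 (arm knowledge irrelevant) | 0 | 0 | 2.5% |
| 0.3 | 0.08 SD | 0.10 to 0.26 | 3.8% |
| 0.5 | 0.14 SD | 0.16 to 0.43 | 5.1% |
| 1 (worst case) | 0.27 SD | 0.33 to 0.86 | about 10.5% |

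With all 15 as the starting number, the worst-case shift for 2 withdrawals is (1.736 + 1.248)/13 = 0.23 SD, so the choice of 12 does not drive the result.

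For scale, the section 1.0 rule for a 500 kcal/day deficit gives 0.5 kg/week × 2 = 1 kg over 14 days. The 30% difference that section 13.0 calls relevant is 0.30 × 3.95 = 1.19 kg or 0.30 × 7.26 = 2.18 kg, using the two one-week losses in Table 2.

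**The case against.** The strongest reply is that the withdrawal bias belongs to a different gap. It exists only if withdrawn subjects are left out, and section 13.0 names no analysis population and no handling of withdrawals. If their Day 14 weights were collected and analysed, this route would largely close whoever knew the arm. That stands, and it is why the effect on weight is conditional.

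Most of section 5.3 is indeed fixed criteria, and the judgment item requires a stated reason. That limits how often discretion operates but does not remove the influence of knowing the arm.

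A reader might infer that discretionary medication titration also tilts the results toward the hypothesis. The documents do not support that. Section 3.0 has, for Day 21, "Medications will be titrated at the study clinician’s discretion in an attempt to attain euglycemia", with the same aim on Day 7. The target is common to both arms, and oral agents are stopped for everyone in the first week. More medication lowers glucose but raises medication use, so titration cannot flatter both outcomes at once.

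A reader might also infer that every deciding clinician could be masked with existing staff. That is not shown. The titrating clinician reviews the log and caloric intake, the log has free-text rows, the stylet is reinserted into a used tube on Days 7 and 14, and subjects know their arm. Research assistants appear only for blood draws, case report forms and data access. Nothing shows that one could supervise a first jejunal bolus, for which section 8.0 warns of dumping symptoms.

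**Conclusion.** The point holds for two tasks: taping waist and hip, and withdrawing on judgment. Waist and hip are directly exposed, by an amount the documents do not allow one to estimate. Weight is exposed mainly through selective withdrawal. Under the stated assumptions this is about 0.14 SD (5.1% false positives favouring the intervention) at a correlation of 0.5, and 0.27 SD (10.5%) in the worst case. These figures rest on an assumed 2 of 12 withdrawn, all in one arm and all left out of the analysis. They are not forecasts, and the worst case should not be read as the expected error rate. Nor do the documents support saying that the weight measurement itself is compromised.

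That existing staff can do these two tasks unaware of the arm is an inference from the matched design and the named roles, not something the protocol states. This is a cheap improvement to a pilot, not a flaw that undermines it.

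**What to change.** **Sections 3.0 and 9.0.** State that weight, waist and hip on Days 0, 14 and 28 are taken by an existing team member who is not told the arm. Open the allocation only after the Day 0 measures, and have other existing staff handle it. Keep entries about flavoring the oral electrolyte solution, which under Table 3 can arise only in the intervention arm, off any page the measurer sees.

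**Section 5.3.** For each judgment withdrawal, record whether the arm was known to the person deciding. Where practicable, have a co-investigator who is unaware of the arm make or confirm non-urgent ones. Safety decisions are never delayed for this.

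Leave medication titration and supervision of the first bolus as the protocol has them.

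**Cost.** Protocol wording and a division of visit tasks among existing roles. Some subjects will reveal their arm, so masking will be partial. The record of whether the arm was known keeps its value even where masking fails.
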